
Furthermore, our expectation is that this difference will be most apparent at 48 hrs. as discussed above with a reduction in narcotic requirements greater than 40% in the continuous catheter TAP group vs. standard single shot Bupivacaine TAP (4.1 mg +/- 3 mg vs. 2.4 mg +/- 1.3 mg Dilaudid). This is based on the assumption that the effects of the local anesthetic control TAP (single shot Bupivacaine) may last up to 24 hrs. At 72 hrs, prior studies, although limited, have not shown a significant difference between TAP block and placebo groups.

c Study Objectives

Primary Aim

The primary aim is to evaluate for any significant difference total post-operative narcotic requirements (Dilaudid) required over 48 hrs. in the continuous catheter TAP block arm vs. the single shot Bupivacaine TAP arm and again the slow release Liposomal Exparel® TAP arm vs. the single shot Bupivacaine TAP arm.

Secondary Aim

The secondary aim will be to evaluate for any significant difference in narcotic requirements at other endpoints such as 24 hrs and at 72 hrs. As discussed before, current studies do not show a significant difference when extrapolated out at those end points, albeit there is very little data at 72 hrs. Other quality indicators of recovery in the three arms such as Visual Analog Scores (VAS) are expected again to be most significantly different at 48 hrs. Other quality measures that will be recorded include incidence and severity of post-operative nausea and vomiting (PONV), time to ambulation, and patient satisfaction with post-operative pain control.

Rationale for the Selection of Outcome Measures

Outcome measurements are based on the assumption that narcotic requirements (i.e. intravenous Dilaudid Patient-Controlled Analgesia [PCA] use) are inversely related to patient satisfaction in regards to their post-operative pain. Additional factors such as VAS, ambulation, performance of daily activities, and anti-emetic pharmaceutical requirements have been chosen as quality indicators in regards to post-operative pain control and dependence on narcotics.

D Investigational Agent

This investigation will use three FDA-approved techniques:

- Bilateral Continuous TAP block via Catheter (One-time bolus of Bupivacaine 0.25% x 20ml per side followed by continuous infusion of Ropivacaine 0.2% 7 ml/hr. per side x 48 hrs.);
- Single Injection TAP block with Exparel® (One-time bolus of Bupivacaine 0.25% x 20 ml followed by Exparel 133 mg per side); and

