Subjects may be withdrawn from the study early due to complications secondary to the surgery itself such as sepsis, bowel dysfunction unrelated to narcotic use, and the need for further exploratory surgery.

Catheter dysfunction due to dislodgment or severe leakage may also precipitate early withdrawal from the study. Bleeding, infection, or need to anti-coagulate may cause premature need to remove the catheters from the patients. In these cases, the data will continue to be recorded as in the other arms; however, time of catheter removal will also be recorded.

Failure to perform an adequate block will also cause withdrawal from the study. Reasons for said failure would include: inability to visualize TAP space on ultrasound and surgical site preventing use of bilateral TAP block.

Failure to place catheter after successful bolus of local anesthetic would move patients from the CTAP group to an un-randomized single shot Bupivacaine arm. Patients will be followed until completion of the study. This data may be analyzed separate or as part of the single shot Bupivacaine group.

Failed block is a withdrawal prior to first study follow up; these patients would need to be replaced or moved to an open un-randomized arm.

Subjects may also be withdrawn from the study if at any time it is determined that they did not meet inclusion exclusion criteria.

iii Subject safety

iv Non-compliance with study visit schedule or study regimen

Subjects may be involuntarily exited from the study for failure to comply with the protocol, failure to attend follow-up visits, or for other reasons. The investigator shall arrange for an exit visit and complete the case report form for the subject to the extent there is data available.

Subjects may voluntarily withdraw from the study at any time without reason. The investigator shall make an effort to obtain an exit visit and complete the case report form for the subject to the extent there is data available. The investigator cannot require that an exit interview take place.

E2.g Data Collection and Follow-up for Withdrawn Subjects

- 1) Reason for withdrawal from study (i.e. block failure, catheter failure, drug toxicity, sepsis, patient request)
- 2) Day of withdrawal from study

Study Drug/Device

E3.a Description

The ON-Q[®] device is considered a non-significant risk device which has been marketed for postoperative pain management since 1998.

Description of Device:

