All post-surgical patients are given a Dilaudid (or the equivalent dose of Morphine if not tolerated) IV PCA with every 10 minutes bolus function following surgery to be initiated immediately upon admission and transfer from the PACU to the floor. A clinician bolus of Dilaudid 0.5 mg every 30 minutes will be made available for additional pain control if needed.

Acetaminophen (Tylenol) will also be made available for treatment of post-operative pain on the floor.

Treatment Regimen

Patients assigned to the study group will randomly be assigned to one of the three arms described above. Patients in the catheter arm will receive a commercially available ON-Q® pain management system filled with 0.2% Ropivacaine. The ON-Q® system consists of an ON-Q® elastomeric infusion pump that will be connected to an end-orifice catheter. Patients in the catheter arm will receive a 20 ml bolus of Bupivacaine via Tuohy needle in the TAP space followed immediately by tunneling of a catheter into the TAP space under ultrasound guidance prior to extubation and complete emergence from general anesthesia. Said catheter will be left to infuse continuous local anesthetic site up to post-operative day 3. Patients in the two (2) single injection arms will similarly receive a bilateral injection of study local anesthetic (Exparel or Bupivacaine) 25-30ml per side in the TAP space prior to the conclusion of surgery under ultrasound guidance. Intra-operatively patients in all three study arms will receive IV fentanyl and IV Acetaminophen 1000mg unless drug allergy or intolerance to either medication.

Initial rescue IV pain medication will be made available similarly in all three study arms according to the institution's protocol for PACU breakthrough pain and will consist primarily of IV Dilaudid (or Morphine equivalent if patient does not tolerate Dilaudid). All post-surgical patients are given a Dilaudid (or Morphine if not tolerated) IV PCA with q10min bolus function following surgery to be initiated immediately upon admission and transfer from the PACU to the floor. A clinician bolus of Dilaudid 0.5 mg every 30 minutes (or Morphine equivalent) will be made available for additional pain control if needed. Tylenol will also be made available for treatment of post-operative pain on the floor.

E3.b Method for Assigning Subjects to Treatment Groups

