Based on the above hypothesis this study will be considered successful in demonstrating superior efficacy relative to control if consumption of opioids postoperative is significantly less among patients randomized to receive a

continuous TAP block via the ON-Q[®] system compared to the patients randomized to receive a single TAP injection of Exparel (liposomal bupivacaine) or single TAP injection of Ropivacaine to treat postoperative pain. However, a finding of no difference between the continuous catheter technique and the Exparel arm would also be considered beneficial to the advancement of post-operative pain control techniques because it would demonstrate similar post-operative pain control can be achieved without the extra time and skill required to place a catheter.

Statistical Methods

Sample Size

The main objective of study is to compare total opioid consumption between the single shot TAP group and the Exparel TAP group with a parallel design. Based on previous studies and internal pilots, the mean total opioid consumption (standard deviation) was 4.1 mg (SD 3 mg) in single shot group and 2.4 mg (SD 1.3 mg) in Exparel TAP group. For the sample size calculation, a standard deviation of 3 is used as a conservative estimate. To detect a difference in mean opioid consumption between treatment groups, 4.1 mg vs. 2.4 mg, a sample size of 49 patients per arm is required to achieve 80% power with a significance level of 0.05 using a two-sided t-test or Wilcoxon rank-sum test depending on normality test. A secondary aim is to examine a difference in mean opioid consumption between the single shot TAP group and continuous TAP group. Allowing for a 10% dropout rate, a total of 159 participants with 53 participants in each arm will therefore need to be recruited into the study. It anticipated that approximately 8 participants per week will be enrolled into this study, thus the estimated accrual time is around 1 year.

Statistical Analysis Plan

All analyses will be conducted on patients following an intention-to-treat principle, including all randomized participants enrolled in three arms, in case of relevant non-compliance to the treatment and/or impossibility to evaluate the endpoints, a per-protocol analysis will also be performed, together with an analysis of non-compliance/non-evaluation.

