Patient characteristics and outcomes data will be summarized by cross-tabulation (categorical variables), quartiles (median, ordinal variables), and mean and standard deviation (continuous variables). Comparisons between groups will use Chi-square test or Fisher's exact test as appropriate for categorical variables and t-test or Wilcoxon rank-sum test as appropriate for continuous variables.

Analyses of primary outcome will examine differences in mean opioid consumption between the single shot TAP group and the Exparel TAP group. Analyses of secondary outcomes will examine differences in mean opioid consumption between the single shot TAP group and continuous TAP group. Treatment groups will be compared using a

student's t-test if data are normal distributed or Wilcoxon rank-sum test if not normal distributed.

The differences in mean opioid consumption across three groups (single shot TAP, continuous TAP, and Exparel TAP) will be examined with a test of means between groups using one-way analysis of variance (ANOVA). A comparison between continuous TAP and Exparel TAP will be performed. A t-test will be used if the observations in each trial arm are normally distributed; if non-normally distributed, then rank-based methods such as Wilcoxon rank-sum test will be employed.

All tests will be two-sided.

The overall incidence of serious adverse events and adverse events and number and proportion of patients reporting such events will be summarized by treatment group. Adverse events will be tabulated and summarized by the number and percentage of subjects who experienced the event.

Missing Outcome Data

Analysis will be conducted as described in prior section. Missing data will not be included in the analysis; however, may lead to an increase in patients recruited into one or more study arms.

Unblinding Procedures

This study is not blinded because it will be obvious to all care givers whether or not the patient received a continuous block with catheters or not.

H Data Handling and Record Keeping

Confidentiality and Security

Data will be collected on the data collection forms located in Attachment L9 and entered into the Oncore ERM study management system.

Data collection forms will be stored at each respective study site within a locked cabinet in a locked research office.

The Oncore ERM study management system is a secure web-based management system that is password-protected. Access to data is role-specific.

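### Catheter-arm patients with failed placement may be analysed apart or as single-shot controls, which contradicts the plan's intention-to-treat rule

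*Combined protocol and SAP*

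**What the plan says.** The rule for failed catheter placement is under Early Withdrawal of Subjects in section E: "Failure to place catheter after successful bolus of local anesthetic would move patients from the CTAP group to an un-randomized single shot Bupivacaine arm". It continues: "Patients will be followed until completion of the study". It then leaves the analysis open: "This data may be analyzed separate or as part of the single shot Bupivacaine group".

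The Statistical Analysis Plan in section G says: "All analyses will be conducted on patients following an intention-to-treat principle, including all randomized participants enrolled in three arms". Where there is relevant non-compliance or an endpoint cannot be evaluated, "a per-protocol analysis will also be performed, together with an analysis of non-compliance/non-evaluation".

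The single-shot group is the comparator for both main contrasts. Section G states: "Analyses of primary outcome will examine differences in mean opioid consumption between the single shot TAP group and the Exparel TAP group". It makes single shot against continuous TAP secondary, whereas the Primary Aim in section C lists both contrasts.

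On dose, the Treatment Regimen says catheter patients "will receive a 20 ml bolus of Bupivacaine via Tuohy needle in the TAP space followed immediately by tunneling of a catheter", and section D gives the same 20 ml per side. Under E3.c, single-shot controls get 30 ml per side of the same 0.25% bupivacaine, or 25 ml if they weigh less than 70 kg.

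**The concern.** Failed placement happens after randomisation and can happen only in the CTAP arm. Any main analysis that takes these patients out of CTAP therefore no longer compares the groups that randomisation formed. The withdrawal section offers two ways to handle them, and neither keeps them where they were randomised.

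Three things are at stake.

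- **Catheter contrast.** Both options leave CTAP with successful placements only. The protocol itself counts the skill and time needed for placement among the catheter's disadvantages, so dropping failures favours the technique on a point the trial is meant to inform.
- **Exparel contrast.** Pooling adds a selected, non-randomised group to the comparator of the contrast that section G calls primary. The bias favours Exparel if these patients use more opioid than controls and works against it if they use less.
- **Timing of the choice.** The wording is permissive and sets no decision point. The trial is described as not blinded, so the choice could be made after the data are seen.

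**Working it through.** **1. The two rules side by side.** ITT with all randomised participants puts a failed-placement patient in CTAP. The withdrawal section puts the same patient in a separate group or in the control group. The per-protocol clause does not reconcile them: it is additional to ITT, and a per-protocol analysis excludes deviating patients rather than counting them in another arm. Pooling is an as-treated rule, and section G names no as-treated analysis.

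**2. Planning figures.** From Sample Size (section G) and section B: control mean 4.1 mg, Exparel and catheter means 2.4 mg each, SD 3 mg, 53 randomised per arm. The planned difference is 4.1 − 2.4 = 1.7 mg. The stated 49 per arm reproduces by the normal approximation: 2 × 3² × (1.960 + 0.842)² / 1.7² = 48.9, rounded up to 49.

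**3. Planned dose.** 20/25 = 80% of the control volume for patients under 70 kg, and 20/30 = 67% for the rest. The concentration is the same, so the milligram ratios are the same.

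**4. Size of the shift.** The documents give neither a failure rate nor opioid use for these patients, so two inputs are assumed:

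- k = 1 to 5 failures among 53 (1.9% to 9.4%);
- mean use in failures of 4.1 + d mg, with d from −0.5 to +0.5.

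Formulas (control minus active):

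- ITT catheter difference = 4.1 − [(53 − k) × 2.4 + k × (4.1 + d)] / 53
- Catheter difference with separate analysis = 4.1 − 2.4 = 1.7
- Pooled catheter difference = [53 × 4.1 + k × (4.1 + d)] / (53 + k) − 2.4
- Exparel shift under pooling = k × d / (53 + k)

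Example, k = 5 and d = +0.5:

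- ITT = 4.1 − (48 × 2.4 + 5 × 4.6)/53 = 1.492
- Pooled = (53 × 4.1 + 5 × 4.6)/58 − 2.4 = 1.743, a shift of 0.251
- Exparel shift = 5 × 0.5/58 = 0.043

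| d (mg) | k | ITT | Pooled | Pooled − ITT | Separate − ITT | Exparel shift, pooled |
|---|---|---|---|---|---|---|
| 0 | 1 | 1.668 | 1.700 | 0.032 (1.9%) | 0.032 (1.9%) | 0 |
| 0 | 5 | 1.540 | 1.700 | 0.160 (9.4%) | 0.160 (9.4%) | 0 |
| +0.5 | 1 | 1.658 | 1.709 | 0.051 (3.0%) | 0.042 (2.4%) | +0.009 (0.5%) |
| +0.5 | 5 | 1.492 | 1.743 | 0.251 (14.7%) | 0.208 (12.2%) | +0.043 (2.5%) |
| −0.5 | 1 | 1.677 | 1.691 | 0.013 (0.8%) | 0.023 (1.3%) | −0.009 (−0.5%) |
| −0.5 | 5 | 1.587 | 1.657 | 0.070 (4.1%) | 0.113 (6.7%) | −0.043 (−2.5%) |

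Percentages are of the planned 1.7 mg. Separate analysis leaves the Exparel contrast unchanged.

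**5. Against sampling error.** The standard error of a difference with SD 3 and 53 per arm is 3 × √(2/53) = 0.583 mg. The largest catheter shift is 0.251/0.583 = 0.43 standard errors; the largest Exparel shift is 0.043/0.583 = 0.07.

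**The case against.** The best defence is that the Statistical Analysis Plan governs. The disputed sentence is permissive and sits in a withdrawal section, and analysing these patients separately could simply be the non-compliance analysis that section G already promises. This has some force for the separate option. It has none for pooling, which no part of section G supports. Nor does the protocol say that section G prevails, and the withdrawal text is the more specific rule for this event, so an analyst could read it as an exception.

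A second objection is that the effect on the primary contrast is negligible. Within the assumed range that is right: at most 0.07 standard errors, and zero without pooling. The larger shifts fall on the catheter contrast. Section G ranks it secondary, but the Primary Aim includes it and the study success criteria rest on the catheter comparison.

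A third is that the 80% and 67% ratios may not describe what failed-placement patients received. E3.c gives only 5 to 10 ml by needle before threading and the rest through the catheter, whereas the Treatment Regimen puts the full 20 ml through the needle. Without a top-up, which the protocol neither orders nor forbids, the dose could be lower than 20 ml. The ratios are therefore planned values and a lower dose is likely but not certain. The conflict with ITT does not depend on them.

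**Conclusion.** The plan is wrong as written. Two sections give incompatible rules for the same patients, nothing says which prevails, and the choice between the two non-ITT options has no stated basis or date.

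That conclusion rests on the text alone. The size of the bias rests on assumed failure counts and opioid use. In the range examined, both options favour the catheter, by up to 0.25 mg when pooled and up to 0.21 mg when analysed separately. The effect on the Exparel contrast is small and its sign is uncertain. More failures, or opioid use further from control, would give larger shifts. The case for a change is the unresolved contradiction and the open choice rather than a demonstrated large bias.

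**What to change.** Under Early Withdrawal of Subjects, delete the option to analyse these patients with the single-shot group. State that they are analysed in CTAP as randomised, in line with section G. Exclude them from any per-protocol analysis, and never count them as single-shot controls, whatever volume they received. Label any separate or as-treated summary a pre-specified supplementary analysis. The sentence that moves these patients can stay as a description of their care, provided the text says it does not change their analysis group.

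The cost is wording, ideally with a matching line in the Statistical Analysis Plan. No extra patients, procedures or data are needed, because these patients are already followed to completion.

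The downside is that the CTAP estimate will include placement failures and may be smaller than the effect of a working catheter. With 5 failures at control-level use, the expected catheter difference is 1.54 mg, and power at 53 per arm and SD 3 falls from about 82% to 74% (two-sided t-test at 0.05). The existing ITT rule already implies that loss.

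### The involuntary-exit rule does not require outcome recording to continue, so patients exited before 48 h can fall out of the intention-to-treat analysis as well as any per-protocol analysis

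*Combined protocol and SAP*

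**What the plan says.** Section E, Early Withdrawal of Subjects, item iv (non-compliance): "Subjects may be involuntarily exited from the study for failure to comply with the protocol, failure to attend follow-up visits, or for other reasons". The third ground has no limit, and the sentence gives no criteria and names no decision-maker. The investigator then arranges an exit visit and must "complete the case report form for the subject to the extent there is data available". Section E2.g, on data collection and follow-up for withdrawn subjects, lists two items: the reason for withdrawal and "Day of withdrawal from study".

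Two other rules under the same heading differ. After premature catheter removal, "In these cases, the data will continue to be recorded as in the other arms". Patients whose catheter could not be placed are followed to the end of the study.

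Section G, Statistical Analysis Plan: "All analyses will be conducted on patients following an intention-to-treat principle, including all randomized participants enrolled in three arms". For non-compliance or endpoints that cannot be evaluated, "a per-protocol analysis will also be performed, together with an analysis of non-compliance/non-evaluation". Per-protocol membership is not defined. Section G, Missing Outcome Data: "Missing data will not be included in the analysis". The same sentence allows extra recruitment into one or more arms.

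The Primary Aim (Section C) measures total opioid use over 48 h; the Analysis Plan in Section G says 72 h. The trial is open. Floor nursing staff are masked only between the two single-injection arms (E2.e, E3.g).

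**The concern.** An intention-to-treat analysis with a per-protocol analysis beside it is informative only if patients who departed from the regimen have outcomes. They then count in the first analysis and can be left out of the second, and the contrast shows how much the departures matter. Item iv allows such a patient to leave the study altogether, with no duty to go on recording. If the exit comes before 48 h and no total is obtained, the missing-data rule removes the patient from the nominal intention-to-treat comparison too. That comparison then becomes, to that extent, a complete-case analysis of the patients who were kept.

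Bias is the main risk. Treatment arm is largely visible, the outcome is opioid use, and one exit ground is unlimited. If exits are related to both arm and opioid use, the estimated difference shifts. Recruiting replacements restores numbers but does not undo the selection.

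**Working it through.** **1. How a patient can be lost.** Three provisions are needed together.

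| Step | Source | Effect |
|---|---|---|
| Exit before 48 h | Section E, item iv | Permitted, grounds open-ended |
| No duty to record opioids after exit | Item iv; E2.g | 48 h total may not exist |
| Missing outcomes excluded | Section G, Missing Outcome Data | Patient leaves the comparison despite intention-to-treat |

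None of these does it alone. A patient exited after 48 h, or whose form is completed from the chart, keeps the 48 h total. If the 72 h horizon of the Analysis Plan applies, the window for loss is longer.

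**2. The plan's own figures.** Sample Size (Section G) gives means of 4.1 and 2.4 mg, SD 3 mg, two-sided 0.05 and 80% power:

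n = 2 × [3 × (1.960 + 0.842) / 1.7]² = 48.9, so 49 per arm, as stated. The plan recruits 53 per arm, allowing for 10% dropout. The planned difference is 4.1 − 2.4 = 1.7 mg.

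**3. Lost power is the smaller issue.** With SD 3 and a 1.7 mg difference (normal approximation), power is 83.1% with 53 evaluable per arm, 80.1% with 49 and 79.3% with 48.

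**4. Illustration of bias.** The documents give no exit rate and do not say which patients would be exited. Both are assumed here. Let opioid use follow a gamma distribution with the plan's mean m and SD, let a fraction f of one arm be exited, and let all exits be drawn at random from that arm's top quartile, with mean M. Then

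observed mean = (m − fM) / (1 − f).

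Single-shot arm (m = 4.1, SD 3): shape (4.1/3)² = 1.87, scale 3²/4.1 = 2.20, M = 8.27 mg.

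| f | Observed mean (mg) | Fall (mg) | Share of 1.7 mg |
|---|---|---|---|
| 2% | (4.1 − 0.165)/0.98 = 4.01 | 0.09 | 5% |
| 5% | (4.1 − 0.413)/0.95 = 3.88 | 0.22 | 13% |
| 10% | (4.1 − 0.827)/0.90 = 3.64 | 0.46 | 27% |

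A lower control mean shrinks the difference, so these exits understate benefit.

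Active arm (m = 2.4, SD 1.3, the plan's Exparel figures): M = 4.19 mg. The same fractions lower that arm's mean by 0.04, 0.09 and 0.20 mg (2%, 6% and 12% of 1.7 mg). Here the difference widens, so benefit is overstated.

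**5. Extreme case under no true difference.** Two arms of 53, normal data, SD 3, with the very highest users removed from one arm only (10,000 simulated trials, two-sided t-test at 0.05):

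| Removed | Bias (mg) | Type I error |
|---|---|---|
| 1 | 0.13 | about 6% |
| 2 | 0.25 | about 8% |
| 3 | 0.35 | about 10% |
| 5 | 0.54 | about 17% |

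This is close to the worst selection possible for each number removed; it is not a forecast.

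**The case against.** A reader might infer that the intention-to-treat and per-protocol sets become the same set, so that comparing them can never show anything. The documents do not support that. Patients whose catheter is removed early, or could not be placed, depart from the assigned regimen and are still followed, so they can count in one analysis and not the other. With per-protocol membership undefined, the overlap cannot be determined at all.

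A reader might also infer that opioid totals will be lost at an unmasked investigator's discretion. Exit is permitted, not required, and the sentence does not say who decides. The form must be completed as far as data exist, and these are inpatient chart data that could often be retrieved. For single-shot versus Exparel, which Section G makes primary, floor nurses are masked, though the provider placing the block is not.

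The link to high opioid use is also an assumption. Single-injection patients receive the whole block before waking, so little regimen is left to break. PCA and clinician boluses are allowed in every arm, so heavy use is not itself non-compliance. The 10% row spends the entire dropout allowance, about 5 of 53 patients, on top-quartile exits from one arm. And if skewed data lead to the planned Wilcoxon test, a shift in means does not directly measure the effect tested.

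All of this limits the size of the concern. It does not close the gap: neither item iv nor E2.g requires recording to continue, and the planned analysis of non-compliance can describe exited patients but cannot supply their missing totals.

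**Conclusion.** The concern holds in a limited form. Item iv and the missing-data rule together allow a patient exited before 48 h without a total to disappear from an analysis described as covering all randomised patients. For those patients, and only those, setting intention-to-treat beside per-protocol is uninformative.

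The size cannot be estimated from the documents. Under the assumed gamma distributions and top-quartile exits of 2% to 10% from a single arm, the shift is 0.09 to 0.46 mg against benefit if exits come from the single-shot arm, and 0.04 to 0.20 mg in favour of benefit if they come from an arm with the plan's Exparel figures. If exits are unrelated to opioid use, or balanced in their effect across arms, little bias follows. The change is worth making because it is nearly free and the damage could not be repaired at analysis.

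**What to change.** In item iv, state that non-compliance is recorded as a protocol deviation and does not end outcome recording. State that opioid use and the other outcomes are collected from the chart to 72 h for every randomised patient unless consent is withdrawn. Remove the open-ended third ground as a reason for ending data collection, and bring E2.g into line. This concerns data collection only and leaves decisions about treatment untouched.

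In Section G, state that these patients remain in the intention-to-treat analysis and are excluded only from the per-protocol analysis, and define per-protocol membership before the data are examined.

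The cost is a short wording amendment and some extra chart abstraction on the existing data form, which already runs from PACU to POD 3. No sample-size input changes.
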